1. INTRODUCTION

Visioneering Technologies, Inc. (VTI) currently has a market cleared multifocal contact lens NatrualVue Multifocal (NVMF), which is a Class II, non-significant risk (NSR) device. This contact lens product is designed for the correction of ametropia including myopia, myopia progression control (outside the US), hyperopia, and/or presbyopia. The optical design of the contact lens creates an enhanced depth of focus (EDOF), which provides clear distance, intermediate, and near vision. This unique optic while expands the depth of the focus, it also generates a significant amount of myopic defocus on the retina in a gentle and discrete way, therefore, it causes minimal visual disturbance.

A. Type of Research

Clinical study for NSR device refinement. This will be a single-masked trial. Subjects will be masked to the design or brand of lenses.

B. Purpose/Objective of the Study

Under this protocol, clinical trials will be undertaken to further optimize the current product design, and evaluate the design with different power or lens configurations including multifocal-toric lenses or other market approved lens materials. The goal of these Research and Development studies is to expand the product line in order to address and serve a larger population.

This protocol will serve as an umbrella protocol, as the clinical studies will be focusing on different aspects of lens performances during difference phase of product development and may conduct at different clinical sites. Minor optimization to the lens design will be made in Phase I, at this phase, shorter follow up evaluations will be made. Other available lenses or lens materials may be used for bench marking purposes. After optimization, the lenses may be dispensed for longer term performances (Phase II).

For each clinical site, the investigator required information (CV, license, site questionnaire, letter of submission) would be submitted to the IRB for review prior to that site recruiting or enrolling subjects. For the duration of the study during dispensing trials, subjects will be required to wear the study lenses for a minimum of 6 hours per day, 5 days per week. Subjects will not be allowed to keep the lenses.

C. Background of the Study

C.1 Normal Vision

For humans to see clearly, light rays entering the eye at various angles must be bent, sometimes referred to as 'refracted', to converge at a single point at the back of the eye. Light rays are first bent by the Cornea, which is the clear front surface of the eye. After the light rays pass through the Cornea, they are bent a second time by the Crystalline Lens, which lies just behind the Cornea. If the eye is focusing the light correctly, the Cornea and the Crystalline Lens bend the incoming light rays so that the light rays converge precisely on the back surface of the eye (the Retina), thereby producing a clear and unblurred image.

It is the ability of the Cornea and Crystalline Lens to bend and converge the incoming light rays precisely onto the Retina, which creates the clear image. If the Cornea and Crystalline Lens bend the light rays too much or too little, the light rays converge either in front of, or behind the Retina, respectively, resulting in a blurry image that requires visual correction.

C.2 Vision Deficiencies

Myopia (Also Known as 'Nearsightedness' or 'Shortsightedness')

Nearsightedness, or Myopia, occurs when the light rays converge in front of the Retina. Myopic people can generally see well for close-up tasks such as reading and computer use, but have difficulty seeing more distant objects clearly without eyeglasses or contact lenses, for example road signs. Other signs and symptoms of uncorrected Myopia include squinting, eye-strain, and headaches, and may also include feeling fatigued when driving or playing sports.

Myopia occurs when the eyeball is too elongated relative to the focusing power of the Cornea and Crystalline Lens of the eye. In Myopia, light rays entering the eye are over-bent (bent at too high an angle relative to the length of the eye) by the Cornea and Crystalline Lens, resulting in the light rays converging in front of the Retina instead of directly on the Retinal surface, thereby creating blur for distant objects. A patient with Myopia is prescribed a 'minus' powered corrective lens, which reduces the angle of the light rays entering the eye, thereby moving the convergence point of the light rays back to the Retina surface.

Myopia typically shows up in early childhood, and progressively worsens until it stabilizes in early adulthood (usually 18-25 years of age).^{1,2} The worsening of Myopia throughout childhood and adolescence is known as Myopia Progression.^{1,2,3} It is currently understood that one of the most significant optical risk factors for Myopia Progression is a condition known as Peripheral Hyperopia.³⁻⁸

In Peripheral Hyperopia, peripheral light rays converge behind the Retina, signaling the eye to grow in length.³⁻⁸ Minus lenses are employed to correct the Myopia at the center of the Retina to provide clear distance vision, but a by-product of this central correction is that the peripheral light rays at the edge of the eye are now moved behind the Retina, which in turn re-establishes a growth signal and consequently, leads to the lengthening of the eyeball.^{4,7} This cycle of central correction leading to eye growth repeats itself over and over, resulting in higher and higher amounts of Myopia.^{4,6,7}

Two additional visual risk factors for Myopia Progression both deal with the amount and accuracy of the eye's ability to focus (called accommodation).^{4,7} When the eye is tasked with focusing for extended periods of near work, which is common in Myopic school-age children, the eye can become stressed and not focus accurately.^{10,15} This lack of accurate focusing can create additional Peripheral Hyperopia that is also thought to contribute to Myopia Progression.^{4,7}

Hyperopia (Also Known as 'Farsightedness')

Hyperopia, or farsightedness, occurs when the light rays converge behind the Retina due to the length of the eye. Hyperopic people can generally see well for distance tasks (for example road signs), but have difficulty seeing close objects clearly without eyeglasses or contact lenses, for example reading books and computer use.

Hyperopia occurs when the eyeball is too short relative to the focusing power of the Cornea and Crystalline Lens of the eye. In Hyperopia, light rays entering the eye are under-bent (bent at too low an angle relative to the length of the eye) by the Cornea and Crystalline Lens, resulting in the light rays converging behind the Retina instead of directly on the Retinal surface, thereby creating blur for close objects. Farsightedness usually is present at birth and tends to run in families as an inherited condition. A patient with Hyperopia is prescribed a 'plus' powered corrective lens, which increases the angle of the light rays entering the eye, thereby moving the convergence point of the light rays forward to the Retina surface.

Presbyopia – Age Related Loss of Near Vision

Presbyopia is characterized by an age-related progressive loss of the ability to see things that are near. Presbyopia usually begins in a patient's 40s. Presbyopia affects close-up tasks such as reading or working at the computer. Most people become presbyopic around the age of 40, even if they have never had a vision problem previously. People who were previously wearing eyeglasses or contact lenses for their Myopia or Hyperopia will also start to notice that their near vision blurs when they wear their usual eyeglasses or contact lenses. Presbyopia typically continues to worsen until around the age of 60.

Presbyopia predominantly arises from a stiffening and weakening of the eye's Crystalline Lens with age. When a person is looking at something up close, light rays enter the eye at a high angle. In a younger person, the eye's Crystalline Lens is flexible and strong, rapidly changing shape to bend those high-angle light rays so that they converge precisely where they are supposed to: on the surface of the Retina (producing a clear image). However, with advancing age, the Crystalline Lens stiffens and weakens, and is unable to sufficiently bend the high-angle incoming light rays. As a result, the incoming light rays converge at a point behind the Retina, thereby creating a blurred image for near vision. A patient with Presbyopia is prescribed a 'relative plus' powered corrective lens (plus relative to their pre-Presbyopia prescription), which increases the angle of the bend, thereby moving the convergence of the light rays forward to the Retinal surface.

For a person who, prior to developing Presbyopia, already has Myopia or Hyperopia due to the length of the eye, Bifocal or Multifocal lenses will be prescribed, containing both an area of 'minus' power (to correct the Myopia) or 'plus' power (to correct the Hyperopia) as well as an area of 'relative plus' power to correct the presbyopia arising from age.

Astigmatism – Light Does Not Come to a Single Focus in the Eye

Astigmatism is another refractive condition that affects how the eye focuses incoming light.

In an eye with Astigmatism, rather than the Cornea and Crystalline Lens causing incoming lights rays to converge on a single focal point on the surface of the Retina, the eye produces multiple focal points either in front of or behind the Retina, or both in front of and behind the Retina. Astigmatism is usually caused by an irregularly shaped Cornea. Instead of the Cornea having a uniformly round shape (like a tennis ball), it has a more oval shape in astigmatic patients (like a football), causing the incoming light to refract unevenly within the eye with no single point of convergence.

Astigmatism can be corrected with a prescription for 'cylindrical' or 'toric' vision correction lenses, which corrects the eye's refraction of incoming light to a single focal point.

C.3 Contact lenses

Contact lenses are widely used for vision correction in individuals who do not prefer to wear eyeglasses full time or undergo corrective surgery, such as LASIK. Worldwide use has been published as high as 125 million global contact wearers.⁹ As published by the US Centers for Disease Control and Prevention (CDC), approximately 40.9 million Americans age 18 and older wore contact lenses in 2014. In particular, daily disposable contact lenses have gained traction and acceptance around the world since being introduced in the 1990s. As reported by Johnson & Johnson Vision Care Companies (2016), the United Kingdom has a larger market share of daily disposable contact lenses than reusable lenses at about 60%. Worldwide it is reported that one in every three lenses that were fitted in Y2015 were for daily disposable use.¹⁰ The introduction of daily disposable lenses offers the lens wearing market an option for quality optics, but without the labor and responsibility of lens cleaning and care. It has been reported that common risk factors for inflammation and infection, such as infrequent storage case replacement, poor case hygiene, and bioburden on the lens and case, may be improved through daily disposable lenses.¹¹⁻¹³

Over 30 years of daily disposable lens use is available demonstrating the acceptable performance and use of hydrogel lenses known as "Etafilcon A". Chalmers et al, reported the rates of adverse events with hydrogel and silicone hydrogel daily disposable lenses in a large postmarket surveillance data collection, known as the "TEMPO" registry.¹⁴ Subjects were any new or experienced soft contact lens wearers age 8 and older who had recently been fit with either 1•DAY ACUVUE TruEye (narafilcon B = SiHyDD) or 1•DAY ACUVUE MOIST (Etafilcon A = HydDD) spherical lenses in both eyes. From these 1171 subjects (approximately half wearing Etafilcon A manufactured lenses and half wearing silicone hydrogel lenses) were assessed for the incidence of lenses related adverse events during a one year period. The rates of corneal infiltrative events were 0.4% and 0.0% for these groups which are significantly lower than the rates reported for reusable soft contact lenses.

C.4 NaturalVue Multifocal Contact lenses and Optimization Plan

VTI lenses are molded, hydrated and sterilized at an FDA inspected and audited facility (Pegavision Corporation, Taiwan). The VTI lens design has received FDA 510k clearance (K150385, 2015, Visioneering Technologies, Inc.). Minor optimization to the lens design will be made (phase I), to include base curves, power profiles, optical zone diameters, edge design, front surface design, toric design and contact lens material performance. None of these minor changes to the design are anticipated to impact the safety and efficacy of the product. After optimization, the lenses will be compared to other available multifocal contact lenses (Phase II).

VTI lenses are of an FDA approved etafilcon-A material, other materials to be evaluated will either be cleared by FDA or passed material safety evaluations per FDA contact lens guidance. The lenses will only be worn on a daily wear basis. All other brands of lenses used will be FDA approved/cleared and will also only be worn on a daily wear basis. If a comparative product is not FDA approved/cleared, separate IRB approval for the use of such product will be required. All lenses will be fitted according to the manufacturer recommended fitting guides, and only those subjects displaying the characteristics of an acceptable lens fit will be dispensed with the lenses.

Data collected under this protocol will include state-of-the-art evaluation methods in contact lens safety and performance testing, presbyopia performance testing and myopia progression control testing; including, but not limited to, vision performance under low-light, and low-contrast conditions, viewing distances or vergences, contrast sensitivity, stereopsis, lens fitting and surface assessments, ocular health and parameter assessments, refraction, and subjective evaluations.

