3. STUDY DESIGN / METHOD / PROCEDURES

A. Summary of the Research Design

The lens optimization trials (Phase I) will involve both non-dispense and dispensing clinical trials. These trials will be prospective and single masked (subject). After an optimized design is determined, the lenses will be dispensed in prospective, masked, cross over trials comparing the lenses to other optimized VTI lens designs and/or to other available contact lenses (Phase II). Phase II trials could be a dispensing study for a period of 1 week each. There will be a follow-up visit during the trial at approximately 2 ± 1 days, and 5 ± 3 days.

All lenses will be dispensed for **daily wear** in this trial.

All data for this trial will be collected using CRFs that will be supplied by the sponsor.

Non-Dispensing Visits	Procedures	Data Collection
Enrollment	
• Biomicroscopic examination.• Baseline ocular health and visual performance evaluations.	
• Subject reads and signs Informed Consent.• Baseline Form
Lens Fitting & performance evaluations (Lens 1)	
• Biomicroscopic examination (if not on the same day of enrollment).• Trial fit lenses.• Visual performance evaluations with lens	
• Lens Evaluation Form• Visual performance Form
Lens Fitting & performance evaluations (Lens 2)	
• Biomicroscopic examination (if not on the same day of enrollment).• Trial fit lenses.• Visual performance evaluations with lens	
• Lens Evaluation Form• Visual performance Form
Exit visit	
• Collect data for End-of-day visit/Trial Exit.	
• Lens End-of-day Visit Form/Trial Exit Form
Unscheduled Visit	
• Clinical exam as necessary	
• Unscheduled Follow-up Visit Form.• Trial Exit Form, as necessary.• Potential Adverse Event Form, as necessary.

Dispensing Visits	Procedures	Data Collection
Fitting / dispensing visit	
• Biomicroscopic examination.• Trial fit lenses.• Dispense lenses.	
• Subject reads and signs Informed Consent.• Baseline Form• Lens Dispense Evaluation

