2-Day Follow-up Visit (2 \pm 1 days)	
• Collect data for 2 Day visit.	
• Lens 2-day Visit Form
1-Week Follow-up Visit (5 \pm 3 days)	
• Collect data for 1-Week visit.• Collect data for Trial Exit.	
• Lens 1-Week Visit Form• Trial Exit Form
Unscheduled Visit	
• Clinical exam as necessary	
• Unscheduled Follow-up Visit Form.• Trial Exit Form, as necessary.• Potential Adverse Event Form, as necessary.

Scheduled Visits

There are three scheduled visits per lens for a dispensing trial:

- Enrollment / dispensing
- Follow-up visit at 2 \pm 1 day
- Follow-up visit at 5 \pm 3 days.

Unscheduled Visits

Visits that are instigated by the subject or requested by the investigator for health or vision-related reasons that occur between scheduled trial visits as specified above are classified as unscheduled visits. In addition, every visit after the trial period that is required because of a finding during the trial is considered an unscheduled visit. For every unscheduled visit the Unscheduled Follow-Up Visit Form must be completed and the reason for the unscheduled visit must be documented.

Missed Visits

Although every effort should be made to comply with the proposed visit schedule, in the event of a missed trial visit, the visit will be documented as missed on the appropriate CRF for that visit.

Exit Visit / Completion of trial

A Trial Exit Form will be completed when each subject completes the trial or is permanently discontinued from the trial. The form will detail the reason(s) for discontinuation.

Study Outcomes:

Performance outcomes:

- Lens fit (biomicroscopy/slit lamp evaluation)
- Other visual acuity tests may include
 - a. Best spherically corrected
 - b. High and low contrast
 - c. Photopic and mesopic
 - d. Distance, intermediate and near
 - e. Extended Depth of Focus (EDOF) curve (+2D to -4D)

- Contrast sensitivity (optional)
- Glare or visual distortion (optional)
- Accommodation performance (optional)
- Questionnaires (optional)

Safety outcomes:

- Best Corrected Visual acuity (High contrast),
- Corneal health as assessed by slit lamp biomicroscopy and other signs and symptoms
- Adverse events

Study Procedures:

Study Treatment

The study method is comprised of the placement of lens(es) on the eye.

Methods:

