1. Following detailed explanation and signing an informed consent form, each subject will perform the following:
 - a. Baseline measurements on visual acuity (Best Corrected Visual Acuity), corneal health, ocular surface topography and anterior segment examination. If the subject meets this study's enrollment criteria,
 - b. The study lens will be placed on the eye.
 - c. The subject will undergo the following evaluations:
 - i. Lens evaluation
 1. Lens position and movement
 2. Surface wettability evaluation (as needed)
 3. Slit lamp fluorescence imaging (as needed)
 4. Tear Exchange evaluation (as needed)
 - ii. Photography/videography from anterior segment examination or lens evaluation (as needed)
 - iii. Vision and Comfort assessment (questionnaire)
 - iv. Uncorrected distance visual acuity (UCVA)
 - v. Habitual distance visual acuity (as needed)
 - vi. Distance best corrected visual acuity (BCVA)
 - vii. Other visual acuity tests may include
 1. Best spherically corrected
 2. Low contrast letters

3. Mesopic lighting conditions
4. Intermediate and near viewing distance
5. Extended Depth of Focus (EDOF) curve (+2D to -4D)

- viii. Glare testing (as needed)
- ix. Distortion test (as needed)
- x. Contrast Sensitivity (optional)
- xi. Add power determination (optional)
- xii. Accommodation range (optional)
- xiii. Accommodative lag (optional)

- d. The lens will be removed at the end of evaluation. Biomicroscopy and BCVA will be conducted as safety monitoring procedures.

All above mentioned testing are either standard clinical test in a routine eye exam or typical clinical/vision research evaluation method.

B. Analysis of Study Results

Descriptive statistics will be calculated for the primary variables in this trial. Where data from control lenses are available, appropriate inferential comparisons will be made.

C. Monitoring

VTI may provide a monitor who will monitor according to Good Clinical Practices (GCPs) the administrative (enrollment, discontinuations, etc.) and safety aspects (incidence and severity of complications, etc.), verify data integrity and assure the continued protection of subjects' rights and welfare.

D. Storage of Data

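### For comparisons of VTI designs that look alike on the eye, the examiner could be masked with coded lenses, but the plan masks only the subject

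*Combined protocol and SAP*

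**What the plan says.** Section 1.A sets the masking for the whole protocol: "This will be a single-masked trial. Subjects will be masked to the design or brand of lenses". Section 3.A says of the Phase I optimisation trials: "These trials will be prospective and single masked (subject". For Phase II it says that "the lenses will be dispensed in prospective, masked, cross over trials comparing the lenses to other optimized VTI lens designs", and adds other available lenses as a further possible comparator. It does not say who is masked in Phase II.

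The Study Outcomes list in section 3.A includes "Lens fit (biomicroscopy/slit lamp evaluation" among the performance outcomes and "Corneal health as assessed by slit lamp biomicroscopy and other signs and symptoms" among the safety outcomes, together with several acuity tests and an EDOF curve from +2D to -4D. The Methods list adds "Lens position and movement" to the lens evaluation. Section 3.B plans inferential comparisons wherever control-lens data exist.

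The documents contain no provision for coded lenses, a masked examiner, a separate unmasked fitter or masked reading of the photographs and videos. They do not say why the examiner is left unmasked, and they describe no order in which lenses are assigned.

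**The concern.** Masking the subject protects what the subject reports. It does nothing for a grade that the examiner assigns at the slit lamp, and it protects a chart score only in part, because whoever runs the test may influence how far the subject is encouraged to read and when the test stops. Questionnaires, which subject masking protects best, are listed as optional in the Study Outcomes.

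Phase I results decide which design goes forward, and Phase II compares that design with others. If the examiner knows which design is on the eye and expects one to do better, a preference between designs could reflect that expectation and not the optics. This deserves attention because some of the comparisons are between two lenses from the same sponsor, where masking the examiner looks practicable.

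**Working it through.** The plan gives no figure to reproduce, so the main check sets the sections side by side.

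1. **Who is masked.** Section 1.A: the subject. Section 3.A, Phase I: the subject. Section 3.A, Phase II: unspecified. Read with section 1.A, the Phase II wording most naturally means the subject again. Nothing extends masking to the examiner.

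2. **What the examiner controls.** Lens fit, lens position and movement, and slit-lamp corneal health are graded by the examiner. Acuity and the EDOF curve are scored from the subject's responses, but an examiner would normally run them. Surface wettability is done only as needed and is not in the outcome list, so it adds little.

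3. **Where masking is feasible.** Section 1.C.4 says VTI lenses come from one named facility. The features it lists for change fall into three groups (the grouping is a design judgement; the documents do not address it):
   - power profile and optical zone diameter: unlikely to identify the design on the eye;
   - base curve, edge and front surface: may show in the fit, the movement or the lens appearance;
   - toric design and material: may well be recognisable.

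   The case for masking is firm for the first group, depends on the particular lens for the second and is weak for the third. It is also weaker for other brands.

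4. **Whether a code alone is enough.** The non-dispensing schedule in section 3.A has a Lens 1 and a Lens 2 visit, and no order is described. If every subject had the same design first, the examiner could work out the code, so coding needs a randomised order to be effective.

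**Illustration of size.** Every input here is an assumption: a two-sided paired t-test at 0.05, no true difference between lenses, a constant examiner shift b in one direction, paired-difference SD s, and n subjects. The documents give no SD, alpha, test or size for any single trial; section 2.F gives only enrolment caps of 600 in total and 100 per site.

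The noncentrality is δ = (b / s) × √n. The false-positive rate is the probability that a noncentral t with n − 1 degrees of freedom and noncentrality δ falls beyond the two-sided critical value, which is 2.045 for n = 30.

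For one letter (b = 0.02 logMAR) and n = 30, with √30 = 5.477:

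| s (logMAR) | δ | False-positive rate |
|---|---|---|
| 0.06 | 0.02/0.06 × 5.477 = 1.826 | 42% |
| 0.08 | 0.02/0.08 × 5.477 = 1.369 | 26% |
| 0.10 | 0.02/0.10 × 5.477 = 1.095 | 18% |
| 0.12 | 0.02/0.12 × 5.477 = 0.913 | 14% |

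At s = 0.08, the one-letter rate is 48% for n = 60 and 70% for n = 100. For half a letter (b = 0.01) at s = 0.08 it is 10%, 16% and 24% for n = 30, 60 and 100. For half a letter at s = 0.12 and n = 30 it is 7%, little above the nominal 5%.

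**The case against.** The strongest reply is that this is an umbrella research and development protocol that declares single masking openly and puts descriptive statistics first. In a VTI-versus-VTI comparison both lenses may be new candidates from the same sponsor, and the documents give the examiner no stated reason to favour either. Expectation is more plausible against another brand, where coding helps least. Acuity and EDOF scores come from a masked subject, and the documents give no scoring or stopping rule, so the route by which an examiner shifts a score is inferred. The false-positive rates rest wholly on assumed inputs.

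Much of this stands. It limits the size and likely direction of the bias and rules out using the illustrated rates as estimates. It does not remove the exposure: slit-lamp and fit grades are the examiner's own, and an examiner can hold a preference between two candidates from one sponsor. A practical limit also stands. Section 1.C.4 requires fitting to the manufacturer's guide, and a coded guide whose content differs between designs could itself identify the lens.

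Three stronger readings are tempting, and the documents do not support them.

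- A reader might infer that examiner masking is feasible for every VTI-versus-VTI comparison. Section 1.C.4 includes toric, front-surface and material changes that may be visible on the eye.
- A reader might infer that the subject mask fails at home because the packs would carry brand names. That argues from silence: section 1.A already commits to masking subjects to design or brand, and pack labelling is how that would be carried out.
- A reader might infer that examiners will favour the new design by a known amount. The documents establish neither the direction nor the size.

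**Conclusion.** The point holds within limits. As written, the plan leaves the examiner free to know which lens is on the eye, and the examiner grades or would normally run much of what is compared. For VTI designs that look alike on the eye, this source of bias could be reduced cheaply. That coding would achieve this is a design inference, not something the documents state.

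The size is unknown. The range of 14% to 42% shows how sensitive a 30-subject paired comparison would be to a constant one-letter shift over assumed SDs of 0.12 to 0.06 logMAR; it does not estimate bias in this trial. The point is an inexpensive improvement, and it does not show that any result would be wrong.

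**What to change.** In sections 1.A and 3.A, state that for VTI-versus-VTI comparisons where the designs cannot be told apart on the eye:

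- the sponsor supplies lenses marked only with a code and power, with any fitting guide issued under the same code;
- each subject wears the lenses in an order randomised for that subject;
- the sponsor holds the key until data lock, with a sealed code break for adverse events;
- subject and examiner are therefore both masked.

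In section 3.A, state who is masked in Phase II. State also that comparisons with visibly different designs (for example toric marks or other materials) or with other brands stay single-masked and are reported as such.

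The cost is label handling, an order list and a code-break step. No visit or procedure is added. If a coded guide would still reveal the design, masking the examiner would need a separate masked assessor, which is a real extra cost; otherwise that comparison should be reported as single-masked.
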